## 1. Background and significance

Complications that occur in laparoscopic surgery are often associated with the initial entry into the peritoneal cavity. The literature reported incidences of Veress Needle (VN) injuries of e.g. 0.31% and 0.23%. In a 2010 national survey of laparoscopic entry techniques in the Canadian General Surgical practice, 57.3% of respondents had either experienced or witnessed a serious laparoscopic entry complication like bowel perforation and vascular injury. As those complications are potentially life threatening and should be avoided at all costs, improving safety of this initial action is paramount.

Based on a bare minimum design approach with focus on function expansion of existing components, a new Safety mechanism was developed for the VN that decreases the risks of VN overshooting. The mechanism works by preventing the puncturing acceleration of the tip of the VN by decoupling the surgeon's hand from the VN immediately after entering the abdomen.

A first prototype of our so called VN+ with force decoupling mechanism proved very reliable in reducing overshooting in an ex-vivo model.

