## 3. Methods

### 3.1 Study design, population and procedures

Study design: open randomized controlled prospective cross over cohort study

Study population: A) group of 10 novices, B) group of 10 surgical, urological or gynaecological residents, C) group of 10 experts consisting of surgeons, urologists or gynaecologists.

Study procedure: After information is given on the purpose and set up of the experiment all participants will be asked to sign an informed consent form.

A video will be shown of the working of a normal VN and of the VN+. After this a detailed video will be shown wherein all basic steps of the procedure are outlined. Then after randomization half of the group will start with a VN and the other half with the VN+. After 5 attempts the groups will switch device and repeat the procedure.

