### 3.2 Procedure and anatomical considerations

After making a small skin incision the insertion of the Veress needles will be:

- at Palmer's point which is 2-3 cm below the left costal margin in the midclavicular line.
- right below the umbilicus after lifting the skin with a clamp

A "grid" will be drawn on the skin. Guided by the grid each attempt will be in a new and unused part of the abdominal wall.

As in total 300 VN(+) insertions have to be performed we will probably need three cadavers

The anatomical region to be used will thus be the abdomen.

In order to see what depth the different needles reach and the possible anatomical structures that will be injured, we will first introduce a laparoscope in the left (or depending on the cadaver the right) lower abdominal quadrant via an open technique and establish pneumoperitoneum through this laparoscope trocar with a pressure that is as low as possible.

Then measurements will take place through recording the number of marks on the needle (previously laser engraved) that are to be seen in the abdomen. The actions will all be filmed and photographed.

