#### 4. Data collection and analysis

In all three groups the measured maximum insertion depths will be calculated in Excel and then any differences between the conventional (VN) and the modified (VN+) groups will be determined with a Mann-Whitney test (SPSS v16, SPSS inc. Chicago, IL) as the data will not be normally distributed. A p-value<0.05 will be considered significant.

All inadvertent tissue or organ damage will be determined and compared between the two types of needles and the groups using a Student T-test (SPSS v16, SPSS inc. Chicago, IL).

A questionnaire (with a Likert scale) will be used to establish the amount of haptic feedback the subjects experience with either the VN or the VN+ at the two different entry sites.

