#### 6. Study Limitations

Limitations:

- different tissue volume and elasticity compared to living tissue
- intraabdominal organs will not react the same way as in living human being
- to be able to determine depth of insertion a small pneumoperitoneum has to be created which in real life situations will not be the case

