#### 7. Ethical Considerations

If the VN+ really does make a significant difference in safety of VN insertion its use will lead to a worldwide reduction in morbidity and mortality caused by VN insertion. A pilot study in an ex-vivo animal (pig) model showed significant positive results. In order to take the step to clinical implementation experiments on human tissue are paramount.

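### If damage is as rare as the injury incidences quoted in section 1, the t-test on tissue or organ damage in section 4 will be undefined or unreliable; damage should be reported as counts with exact limits

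*Combined protocol and SAP*

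**What the plan says.** Section 1 motivates the study with clinical injury rates, both percentages: "The literature reported incidences of Veress Needle (VN) injuries of e.g. 0.31% and 0.23". It gives no denominator, operator experience or injury definition for them, and the plan does not adopt them as rates expected in the study.

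Section 3.1 defines the participants as "A) group of 10 novices, B) group of 10 surgical, urological or gynaecological residents, C) group of 10 experts". Each participant uses both needles: "After 5 attempts the groups will switch device and repeat the procedure". Section 3.2 gives the only size figure: "As in total 300 VN(+) insertions have to be performed we will probably need three cadavers".

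Section 2 lists potential safety issues among the secondary objectives; the primary objective concerns overshoot. Section 4 says of damage: "All inadvertent tissue or organ damage will be determined and compared between the two types of needles and the groups", with Student's t-test as the method. It gives no expected damage rate, power, confidence interval or rule for reading zero or very few events. The limitations in section 6 concern tissue properties, organ behaviour and the pneumoperitoneum. They do not mention that injuries may be too rare to compare.

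**The concern.** The only planned direct comparison of harm is a significance test on an event that, by the only rates in the document, may hardly occur in a study of this size. Two problems follow. First, a t-test on a nearly empty 0/1 outcome either cannot be computed or gives a p-value that should not be trusted. Second, an empty or non-significant result could be reported as no damage or no difference and taken as reassurance, because nothing in the plan says how little it would mean. What is at stake is the interpretation of a secondary outcome, not the depth result.

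**Working it through.** **Inputs.** 30 participants (three groups of 10) and 5 attempts per needle, from section 3.1. Total of 300 insertions, from section 3.2. Injury incidences of 0.31% and 0.23%, from section 1. Assumptions: damage is scored yes/no per insertion, since section 4 does not give the unit of analysis; tests are two-sided; insertions are independent.

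**The plan's own figure.** 30 × 5 × 2 = 300, which agrees with section 3.2. That is 150 insertions per needle, and 10 × 5 = 50 per needle in each experience group.

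**Expected events, n × p.**
- Per needle: 150 × 0.0031 = 0.465 and 150 × 0.0023 = 0.345.
- Per needle within one experience group: 50 × 0.0031 = 0.155 and 50 × 0.0023 = 0.115.

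**Chance of no event, (1 − p)^n.**
- Standard needle only: 0.9969^150 = 0.628 and 0.9977^150 = 0.708.
- Both needles at the same rate: 0.9969^300 = 0.394 and 0.9977^300 = 0.501.

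The 63% and 71% describe the standard needle alone. They apply to the whole study only if VN+ prevents every injury.

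**How the t-test behaves.** With no events both sample variances are zero, so the statistic is 0/0 and undefined. With 4 events v 0:
- the difference in proportions is 4/150 = 0.02667;
- the sample variance in the arm with events is 4 × (1 − 0.02667)/149 = 0.02613, and it is zero in the other arm;
- the standard error is √(0.02613/150) = 0.0132;
- t = 0.02667/0.0132 = 2.02 on 298 degrees of freedom, p = 0.044.

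Fisher's exact test on the same table gives p = 0.12. It falls below 0.05 only at 6 v 0 (p = 0.030; 5 v 0 gives 0.060). So the planned test would declare significance on a table that an exact test does not.

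**Can either threshold be reached at the quoted rates?** For 4 or more events in 150 (one minus the binomial probabilities of 0 to 3), the chance is 0.13% at 0.31% and 0.04% at 0.23%. For 6 or more it is about 9 and 2 in a million. Power is negligible with either test, even if VN+ prevented every injury.

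**What zero events would show.** The exact one-sided 95% upper limit is 1 − 0.05^(1/n). For 0/150 it is 1.98%, which is 1.98/0.31 = 6.4 and 1.98/0.23 = 8.6 times the quoted incidences. For 0/50 it is 5.8%.

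**If damage is commoner (assumed rates).** Power of a two-sided Fisher test at 150 v 150 is 77% for 5% v 0%, 30% for 10% v 5%, and 63% for 20% v 10%. Clustering within operators, and within what will probably be three cadavers, is not allowed for in any figure here.

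**The case against.** The strongest objection is that the benchmark does not match the outcome. The quoted incidences are clinical background. The study counts all inadvertent tissue or organ damage, seen through a laparoscope, in cadavers, with a third of the operators novices. The rate could be well above 0.31%, and the sensitivity figures show that the comparison would then carry some information. This stands: the shortage of events is conditional on the quoted rates and is not a prediction. It does not rescue the plan, which offers no other rate and no way of handling a sparse result.

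A reader might also infer that section 7 makes a safety claim that the damage data cannot bear. The text does not support that. Section 7 is a conditional rationale (the sentence begins "If the VN+ really does make a significant difference in safety of VN insertion its use will lead to a worldwide reduction in morbidity and"). It does not say that the damage comparison will establish the condition, and nowhere does the plan say that absence of damage proves safety. The misreading is a risk left open, not a statement made.

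Nor can one infer that the pneumoperitoneum lowers the damage rate. Section 6 says "to be able to determine depth of insertion a small pneumoperitoneum has to be created which in real life situations will not be the case", which discloses a departure from practice without giving a direction of effect.

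Finally, safety is a secondary objective, loosely worded, and can be addressed by description without a powered test. That is true, and it supports descriptive reporting in place of the planned test.

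**Conclusion.** The point holds in conditional form. If damage is about as rare as the incidences in section 1, each needle would produce about a third to a half of an event in 150 insertions. The t-test would then probably be undefined or rest on one or two events, and where it first reaches significance (4 v 0, p=0.044) an exact test gives 0.12. An empty or non-significant comparison would leave damage rates of up to about 2.0% per needle, or 5.8% per needle within an experience group, unexcluded. These limits assume independent insertions and are therefore optimistic. At higher cadaver rates the shortage of events eases, but the plan gives no such rate. The comparison of insertion depth is unaffected. It would go too far to conclude that no events will occur, or that the plan claims a safety result it cannot deliver.

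**What to change.** **Section 4.** Replace the t-test on damage with descriptive reporting: number of damage events over number of insertions for each needle, overall and by experience group, each with an exact binomial upper limit. Note beside the limits that they are optimistic because insertions are clustered within operators and cadavers.

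**Section 6.** Add that few or no damage events do not show that VN+ is safe or that the two needles are equally safe.

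**Optional.** Contact of the needle tip with an organ could be read from the planned film as an exploratory item. The documents give no rate for it, and the reading would be subjective in an open study, so it should not be relied on as the main safety comparison.

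Section 7 needs no change. The cost is a few sentences, ideally settled before data collection. The downside is small: no p-value for damage and a more modest safety conclusion.

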## 2. Study objective(s):

The purpose of the study is to repeat our previous ex-vivo experiments in a real-life laparoscopic set up in a human/cadaveric model.

The primary objective will be to establish what the amount of benefit will be in using the VN+ as compared to a standard VN. We need to measure in a life-like situation what the reduction of the overshoot will be while in the hands of novices, junior residents and experts to validate the learning curve. Other secondary objectives are establishing the amount of haptic feedback of the VN+ compared to the standard VN and potential safety issues. All the practical investigations will need to take place in the ASC. Data study and technical alterations on the instruments will take place at the TU Delft.

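### The learning-curve aim has no matching depth analysis: section 4 uses neither attempt number nor a comparison of the needle benefit between experience groups

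*Combined protocol and SAP*

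**What the plan says.** Section 2 states that overshoot reduction is to be measured "in the hands of novices, junior residents and experts to validate the learning curve". It does not define the term.

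Section 3.1 describes an "open randomized controlled prospective cross over cohort study" with "A) group of 10 novices, B) group of 10 surgical, urological or gynaecological residents, C) group of 10 experts". Half start with the VN and half with the VN+, by randomisation. "After 5 attempts the groups will switch device and repeat the procedure". Section 3.2 gives two entry sites, a fresh part of the abdominal wall for each attempt, probably three cadavers, and the total: "As in total 300 VN(+) insertions have to be performed".

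On depth, section 4 says "In all three groups the measured maximum insertion depths will be calculated in Excel" and then that "any differences between the conventional (VN) and the modified (VN+) groups will be determined with a Mann-Whitney test". It does not say how the five repeats per person enter the test, or whether the test is run once overall or once per experience group. Attempt number, period and order are not mentioned. The only comparison that names the groups as well as the needles is for tissue or organ damage. Section 6 does not list practice effects as a limitation.

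**The concern.** The aim can be read in two ways, and each needs its own contrast.

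- **Change with use:** does the VN+ benefit grow, shrink or hold over attempts 1 to 5? This needs depth by attempt number for each needle.
- **Difference by experience:** is the benefit larger in novices than in residents or experts? This needs the VN minus VN+ difference compared between groups.

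The design produces data for both, and the analysis section uses them for neither. At stake is a stated part of the objective. A benefit that fades after the first few uses and one that persists have different practical meanings for a safety device, as do a benefit confined to novices and one shared by all. If attempt number, site and cadaver are not logged at the time, they would have to be recovered from the film afterwards.

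**Working it through.** **1. The plan's count (sections 3.1 and 3.2).** 3 groups × 10 people × 2 needles × 5 attempts = 300, as stated. Each needle has 10 × 5 = 50 insertions per group. Of these, 5 × 5 = 25 come from people who have not yet used the other needle; over all groups that is 15 × 5 = 75 per needle.

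**2. Change with use.** A Mann-Whitney test depends only on which values belong to which needle, not on their sequence. On simulated data (10 people, 5 attempts per needle), shuffling attempts within each person left the p-value at 0.000128 both times. If one summary per person is used instead, the sequence is lost before the test. To illustrate with invented values, benefits of 10, 8, 6, 4 and 2 mm average (10+8+6+4+2)/5 = 6 mm, the same as a constant 6 mm.

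**3. Difference by experience.** The quantity needed is (VN − VN+ in one group) − (VN − VN+ in another). One overall test does not give it. Nor do three separate tests: significance in one group and not in another does not show that the benefits differ.

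**4. Practice carried to the second needle.** Assume depth falls by s per attempt over a person's ten attempts, starting at 0. The mean is −2s in period 1 and −7s in period 2, a drop of 5s. For s = 0.05, 0.10 or 0.20 SD this is 0.25, 0.50 or 1.00 SD.
- Needle contrast: half of each needle's data come from each period, so both needles average (−2s − 7s)/2 = −4.5s and the bias is 0.
- Attempt curve for one needle, ignoring period: at attempt k it averages −s(k−1) and −s(k+4), which is −s(k+1.5). This lies 2.5s below the first-use curve, with the same slope. If practice instead stopped after the fifth insertion, the slope would average −s and 0, giving −s/2, half the first-use slope.

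**5. Precision of the added terms.** The documents give no SD, so results are in units of the within-person SD, assuming independent residuals and a common slope. For attempts 1 to 5, Sxx = 4+1+0+1+4 = 10. The SE of one needle's slope is 1/√(10n). The multiplier for 80% power at two-sided 0.05 is 1.960 + 0.842 = 2.80.
- First period only, n = 15 per needle: SE 0.082, detectable slope 0.23. The difference between needles needs 0.23 × √2 = 0.32 per attempt, or about 4 × 0.32 = 1.3 SD from attempt 1 to attempt 5.
- All 300 insertions, n = 30 per needle: SE 0.058, detectable slope 0.16. The difference needs 0.16 × √2 = 0.23 per attempt, or about 0.9 SD over the five attempts. This assumes the same slope in both periods.
- Needle benefit between two groups: each person's difference has variance 1/5 + 1/5 = 0.4, a group mean of 10 has 0.04, and a difference of two groups has 0.08. The SE is 0.283 and the detectable difference 2.80 × 0.283 = 0.79 SD. Variation in benefit between people would raise this.

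**6. Entry site.** Five attempts per needle at each of two sites would give 600 insertions, so 300 leaves five in all. If a person uses both sites, five cannot split evenly (3 and 2, say), and no site order is given. If everyone began at the same site, attempt would be mixed with site.

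**The case against.** The strongest reply is that section 2 attaches the learning curve to experience level, so the five attempts are simply replicates and no result by attempt was promised. That is a fair reading, and the needle results by group would then bear on the aim descriptively. It does not close the gap, because no comparison of the depth benefit between groups is planned.

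A reader might infer several stronger things that the documents do not support:

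- That the five attempts are pooled as separate values. Section 4 does not say; what can be said is that attempt number is not used.
- That carry-over biases the main needle comparison. With starting needle randomised half and half, a practice effect that acts alike in both orders cancels (step 4). Bias would need unequal transfer between the needles, about which the documents say nothing.
- That the groups' prior experience is mostly with the conventional needle. Participants' device history is not described.

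It is also fair to say that the interaction estimates will be imprecise. That is a reason to report them as estimates, not to leave the aim without an analysis.

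**Conclusion.** The concern stands in this form: followed exactly, section 4 leaves the learning-curve aim of section 2 without a depth analysis on either reading. This rests on the text alone and does not depend on how the repeats are handled.

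It does not undermine the primary question, the amount of benefit of the VN+ over the VN. Nor does it follow that the data could never inform the aim: the planned 300 insertions can, with modest precision. The detectable differences in step 5 rest on independent residuals, a common slope and a normal approximation, and cannot be put in millimetres because no SD is given. The plan should be amended before the first insertion; the change is cheap.

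**What to change.** - **Recording and procedure (section 3):** log attempt number, period, entry site and cadaver for every insertion. Vary or balance site order between participants so that attempt is not confounded with site.
- **Analysis (section 4):** add a mixed model of depth on all 300 insertions with needle, attempt, period, site, cadaver and experience group, participant as a random effect, and needle-by-group and needle-by-attempt terms. Report both interactions with 95% intervals.
- **Supporting displays:** give first-period-only curves as a sensitivity analysis, and attempt curves by experience group descriptively (5 people per needle per group in the first period).
- **Wording (section 2):** state that the needle-by-group result describes prior experience and the needle-by-attempt result describes change with use.

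The cost is a little more recording, some organisation of site order, and one further analysis of insertions already planned and filmed. Intervals for the interactions will be wide, so they should be presented as estimates and not as confirmatory tests.

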## 3. Methods

### 3.1 Study design, population and procedures

Study design: open randomized controlled prospective cross over cohort study

Study population: A) group of 10 novices, B) group of 10 surgical, urological or gynaecological residents, C) group of 10 experts consisting of surgeons, urologists or gynaecologists.

Study procedure: After information is given on the purpose and set up of the experiment all participants will be asked to sign an informed consent form.

A video will be shown of the working of a normal VN and of the VN+. After this a detailed video will be shown wherein all basic steps of the procedure are outlined. Then after randomization half of the group will start with a VN and the other half with the VN+. After 5 attempts the groups will switch device and repeat the procedure.

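### The depth comparison uses an unpaired Mann-Whitney test in a randomised crossover, so it ignores participant, device order and entry site; as a smaller point, no rule matches the site split between needles

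*Combined protocol and SAP*

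**What the plan says.** Section 3.1 sets out a randomised crossover in three groups of 10: novices, residents and experts. Randomisation decides only which needle comes first; then "After 5 attempts the groups will switch device and repeat the procedure".

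Section 3.2 lists two entry sites, Palmer's point and "right below the umbilicus after lifting the skin with a clamp". It gives the size of the study ("As in total 300 VN(+) insertions have to be performed") and measures depth by "recording the number of marks on the needle". Each attempt must use a fresh grid position, but no number of attempts per site is given.

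Section 4 covers depth in each experience group: "In all three groups the measured maximum insertion depths will be calculated in Excel". For the comparison of needles, its plan is that "any differences between the conventional (VN) and the modified (VN+) groups will be determined with a Mann-Whitney test", the reason being "as the data will not be normally distributed". It mentions no pairing, device order, site or participant for depth, and does not state the unit of analysis. Site comes up again only for the haptic questionnaire, which asks about feedback "with either the VN or the VN+ at the two different entry sites".

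**The concern.** A crossover is chosen so that each participant serves as his or her own control. An unpaired test gives that up: differences between participants and between entry sites stay in the error term. The sites differ in technique, since the skin is lifted at only one of them. Section 2 makes the amount of benefit the primary objective and wants it in each experience group, where there are only 50 insertions per needle.

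There is also a validity question. Ten insertions by one pair of hands are not ten independent observations. If some participants gain more from VN+ than others, an insertion-level test understates the uncertainty of the average benefit.

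The split over sites is a separate matter. Five attempts cannot be halved, and nothing requires the mix to be the same for both needles. This cannot be repaired once the insertions are done.

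**Working it through.** **1. The plan's own figure.** 30 participants x 2 needles x 5 attempts = 300, as stated. Five attempts per site per needle would need 600, so five is the whole allotment per needle.

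**2. Assumptions.** The documents give no SD, site difference, participant variation or device effect. Assumed: normal depths with SD 1 within participant and site; site difference D = 0, 0.5, 1 or 2; participant SD s = 0 or 0.5; device effect 0.35 overall (150 v 150 insertions) or 0.6 per group (50 v 50); two-sided 0.05; insertions as the unit; same split on both needles.

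**3. Mechanism.** The unpaired test takes the spread of depth as S = √(1 + D²/4 + s²). Under a matched split, site and participant cancel from the actual VN minus VN+ difference, whose standard error is √(2/150) = 0.1155. The test therefore rejects a true null at about 2[1 − Φ(1.96 S)]. With s = 0:
- D = 0.5: S = 1.031, rate 0.043
- D = 1: S = 1.118, rate 0.028
- D = 2: S = 1.414, rate 0.006

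Simulated Mann-Whitney rates are 0.042, 0.029 and 0.004.

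**4. Simulated Mann-Whitney power** (reruns move these by up to about 0.02):

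| | D = 0 | 0.5 | 1 | 2 |
|---|---|---|---|---|
| Overall, s = 0 | 0.84 | 0.82 | 0.77 | 0.54 |
| Overall, s = 0.5 | 0.77 | 0.75 | 0.70 | 0.47 |
| Per group, s = 0 | 0.82 | 0.81 | 0.75 | 0.50 |
| Per group, s = 0.5 | 0.77 | 0.74 | 0.69 | 0.45 |

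**5. Skewed whole marks** (lognormal, rounded; overall, s = 0). Mann-Whitney 0.98, 0.96, 0.89 and 0.68 at the four values of D. An aligned-rank test stratified by participant and site gives 0.94 to 0.95 throughout. A linear model, which works on means, gives 0.84 to 0.85.

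**6. Device effect varying between participants** (SD τ, no average effect, D = 0, s = 0). The true variance of the mean difference is (τ² + 2/5)/30. The unpaired test takes (1 + τ²/2) x 2/150.
- τ = 0.5: 0.0217 v 0.0150, ratio 1.44, false-positive rate 2[1 − Φ(1.96/√1.44)] = 0.10
- τ = 1: 0.0467 v 0.0200, ratio 2.33, rate 0.20

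Simulation gives about 0.12 and 0.19. Site and participant differences pull the other way: with D = 1 and s = 0.5 the rates are about 0.05 and 0.13.

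**7. The split.** If every participant did 3/2 with one needle and 2/3 with the other, the raw difference would shift by (3/5 − 2/5) x D = 0.2 D. Overall false-positive rates would be 0.12, 0.33 and 0.80 at D = 0.5, 1 and 2. If the split varies at random, they are 0.042, 0.028 and 0.010 (3/2 or 2/3 per set of five) or 0.047, 0.049 and 0.060 (site random per attempt).

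**8. Paired alternative.** A participant's mean difference has variance 2/5, so the standard error over 30 participants is √(0.4/30) = 0.1155, with no S attached. Comparing period differences between the two device orders by ranks gives a false-positive rate of about 0.04 to 0.05 under varying device effects and period effects. Overall power is about 0.78 to 0.82 at every site or period effect tried. Within a group it is 5 v 5 participants: the largest exact two-sided level not above 0.05 is 8/252 = 0.032. Power there is about 0.62, against 0.69 for Mann-Whitney (D = 1, s = 0.5).

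**The case against.** **The sizes are all assumed, and the large losses need a large site difference.** This stands. Nothing in the documents supports a shift of 1 to 2 SD, and at 0.5 SD the loss on normal data is about 0.02.

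**On the data the plan expects, the planned test may be the stronger one.** This stands in part. With skewed marks and no participant differences, Mann-Whitney slightly beats the aligned-rank test at D = 0 and 0.5 (0.98 and 0.96 v 0.95). Any analysis of participant means gives up more, as the linear-model figures show. The case for pairing is therefore fit to the design and error control, not a guaranteed gain in power. Non-normality is a reason for ranks; it is not a reason to drop the pairing.

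**Each participant might use one site only.** The protocol does not exclude this. A reader might infer from the two listed sites that each participant must cover both within five attempts. The questionnaire wording and the 300 total make that probable, but no sentence states it. The unpaired test ignores participant and device order either way.

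**Repeating the procedure suggests the same mix on both needles.** It does lean that way. A reader might infer that the unfixed split causes the power loss or makes the comparison biased. Neither is supported: every loss in the table assumes a matched split, and bias needs a systematic mismatch that nothing in the documents suggests.

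**Depths might be averaged per participant before testing.** The unit is not stated. The false-positive figures in step 6 apply only if insertions are treated as independent, but an unpaired comparison of participant means would still discard the pairing.

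**Conclusion.** The concern holds in this form: the named depth test does not fit the named design. Under the stated normal-data assumptions, overall power falls from about 0.84 to 0.77 at a 1 SD site difference and to about 0.70 if participants also differ with SD 0.5. The loss is negligible if both differences are small. The error can also go the other way, with false positives of about 0.12 to 0.19 if the device effect varies between participants with SD 0.5 to 1 and neither site nor participant differences offset it. The direction is therefore unknown in advance.

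The missing rule for the site split is a separate, smaller risk. It deserves a line in the protocol because it cannot be corrected afterwards. The 0.80 worst case requires all 30 participants on opposite splits and a 2 SD site difference; it should not be read as the expected error rate.

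The change should be made. Confidence is medium, because the mismatch is plain in the text but its size depends on quantities that the documents do not give.

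**What to change.** 1. **Sections 3.1 and 3.2.** Preassign each participant's site sequence and use the same sequence with both needles. In each group of 10, five participants do three attempts at Palmer's point and two below the umbilicus, and five do the reverse. Within the two device-order arms of five, divide these 3:2 in one arm and 2:3 in the other. This gives 5 x 3 + 5 x 2 = 25 insertions per needle per site in each group, 75 overall, and keeps the total at 300. If one site per participant is intended, say so.
2. **Section 4, primary analysis.** Replace the Mann-Whitney test on insertions with a participant-level paired analysis. Take each participant's mean VN minus VN+ depth and compare period differences between the two device orders by a rank test stratified by experience group. Report the mean difference in marks with a 95% CI.
3. **Within each group of 10.** Report the estimate and 95% CI. Report depth by site descriptively.
4. **Sensitivity.** Use the aligned-rank test stratified by participant and site here only. It keeps power on skewed marks, but its false-positive rate is about 0.07, 0.12 and 0.23 if the device effect varies between participants with SD 0.3, 0.5 and 1. Do not use a signed-rank test that ignores device order: its power falls to about 0.18 under a 1 SD period effect.

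**Cost.** An allocation sheet and no extra insertions. On normal data, overall power is about 0.04 lower if neither site nor participant matters. Expect a larger loss against Mann-Whitney on strongly skewed marks when site differences are small. Per-group test power is lower (about 0.62 v 0.69 in the case in step 8), which is why item 3 asks for estimates.
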